### **12.2. Recording Adverse Events**

All AEs will be reported from the first dose of study drug through the EOT visit (30 ±7 days following the last day of study treatment). Only treatment-related AEs will be captured from

EOT through Follow-up visits. All treatment-emergent SAEs will be followed until resolution or stabilization.

Whenever possible, a diagnosis should be given when signs and symptoms are due to common etiology (e.g., cough, runny nose, sneezing, sore throat, and head congestion should be reported as “upper respiratory infection”). AE reporting and severity grading will be assessed using the NCI Common Toxicity Criteria (CTC), Version 4.03 (June 2010). For those events without assigned CTCAE grades, the recommendation on page 1 of the CTCAE that converts mild, moderate and severe into CTCAE grades should be used. A copy of the NCI CTC is available online at: <http://evs.nci.nih.gov/ftp1/CTCAE/About.html>.

The causal relationship to study treatment will be determined by the Investigator according to best medical judgment, as follows:

- Definitely related: This category applies when, after careful medical consideration, there is almost no consideration of other causation.
- Probably related: There is a clinically plausible time sequence between onset of the AE and study treatment administration. The AE is unlikely to be caused by a concurrent and/or underlying illness, other drugs, or procedures. If applicable, the AE follows a clinically consistent resolution pattern upon withdrawal of study drug.
- Possibly related: There is a clinically plausible time sequence between onset of the AE and study treatment administration, but the AE could also have been caused by the concurrent/underlying illness, other drugs, or procedures. Information regarding study drug withdrawal may be lacking or unclear. “Possible” should be used when study treatment administration is one of several biologically plausible causes of the AE.
- Unlikely related: The AE is most likely due to a non-study-treatment-related cause. However, association with the study treatment cannot be completely ruled out.
- Unrelated: Another cause of the AE is most plausible and a clinically plausible temporal sequence is inconsistent with the onset of the AE and study treatment administration and/or a causal relationship is considered biologically implausible.

For the purpose of regulatory reporting requirements, causal relationships of definite, probable, and possible will be considered treatment-related, while unlikely and unrelated will be considered not treatment-related.

### **12.3. Serious Adverse Events**

An SAE is any AE or suspected adverse reaction that is considered “serious” if, in the view of either the Investigator or Sponsor, it results in any of the following outcomes:

- Is fatal;
- Is life-threatening (defined as an immediate risk of death from the event as it occurred);
- Requires in-patient hospitalization or prolongation of existing hospitalization (Exception: Hospitalization for elective treatment of a pre-existing condition that did

not worsen during the study and is not considered an AE. Note: Complications that occur during hospitalization are AEs and if a complication prolongs hospitalization, then the event is serious);

- Results in persistent or significant disability/incapacity, or substantial disruption of the ability to conduct normal life functions;
- Is a congenital anomaly/birth defect, or;
- Though not included in the above definitions, may be considered serious when, based upon appropriate medical judgment, they may jeopardize the subject and may require medical or surgical intervention to prevent one of the outcomes listed in this definition.

Examples of important medical events which may meet the definition of a SAE include: intensive treatment in the emergency room or at home for allergic bronchospasm, certain abnormalities (e.g., blood dyscrasias), convulsions that do not result in hospitalization, or the development of drug dependency or drug abuse.

Grade 4 laboratory abnormalities will not be reported as SAEs except in those cases when the abnormality is associated with a clinical diagnosis, which is a recorded SAE.

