### **7.2. Secondary Objectives**

- To evaluate PFS, median PFS, and PFS at 6 months (PFS6).
- To evaluate OS.
- To evaluate the disease control rate (DCR) and duration of response (DOR).
- To evaluate the incidence and severity of AEs, serious adverse events (SAEs), and other safety parameters in subjects receiving CUDC-907.
- To characterize the pharmacokinetics (PK) of CUDC-907.

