## **12.4. Reporting of Adverse Experiences, Serious Adverse Experiences, Serious and Unexpected Adverse Experiences**

### **12.4.1. Reporting Adverse Events and Serious Adverse Events to the Sponsor**

All SAEs, regardless of relationship to the study treatment, must be reported to the Sponsor within 24 hours of the Investigator becoming aware of the event. Written SAE notification must follow within the 24-hour reporting timeframe, via an SAE Report submitted to Novella Clinical Safety Management via email at [[contact]](mailto:[contact]) or by fax at [name]. Where appropriate, follow-up SAE reports must be submitted by the Investigator as new information becomes available. All treatment-emergent SAEs should be followed until resolution, return to baseline or stabilization.

If the Investigator becomes aware of safety information involving a subject who participated in the study that appears to be drug related, even after an individual subject has completed the study, this should also be reported to the Sponsor.

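### Section 12.3 bars Grade 4 laboratory abnormalities from SAE reporting without exempting those that themselves meet a seriousness criterion, which conflicts with its own criteria and with Section 12.4.1

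*Combined protocol and SAP*

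**What the plan says.** Section 12.3 makes an adverse event serious if "in the view of either the Investigator or Sponsor, it results in any of the following outcomes". Two of those outcomes matter here: "Is life-threatening (defined as an immediate risk of death from the event as it occurred" and "Requires in-patient hospitalization or prolongation of existing hospitalization". The only exception attached to the hospitalization criterion concerns elective treatment of a pre-existing condition. Among its examples of important medical events that may qualify, the section names "certain abnormalities (e.g., blood dyscrasias".

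The section closes with a rule for one class of event: "Grade 4 laboratory abnormalities will not be reported as SAEs except in those cases when the abnormality is associated with a clinical diagnosis". The sentence goes on to limit its exception to an abnormality "associated with a clinical diagnosis, which is a recorded SAE".

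Section 12.4.1 sets the duty to report: "All SAEs, regardless of relationship to the study treatment, must be reported to the Sponsor within 24 hours". It contains no exception for laboratory findings.

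Section 7.2 lists as a secondary objective: "To evaluate the incidence and severity of AEs, serious adverse events (SAEs), and other safety parameters in subjects receiving CUDC-907". Section 14.4.4 plans a table of serious treatment-emergent adverse events (TEAEs).

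**The concern.** The seriousness criteria look at outcome. The closing sentence looks at grade and type of finding, and the way back into SAE reporting is a second recorded SAE, not the criteria themselves. A subject admitted for a Grade 4 laboratory adverse event, with no associated diagnosis recorded as an SAE, therefore falls under two opposite instructions a few lines apart.

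Such events are foreseeable. Section 6.3.1 lists thrombocytopenia, neutropenia and hyperglycemia among drug-related Grade 3 or 4 events in the Phase 1 study. Table 2 provides for Grade 4 thrombocytopenia and Grade 4 anemia that need transfusion, and for symptomatic Grade 4 hyperglycemia.

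At stake are the 24-hour report to the Sponsor, the investigator's SAE report to the IRB (Section 12.4.2), and the count in the serious TEAE table. Where the closing sentence is applied, the error runs one way: serious events are left out.

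**Working it through.** No arithmetic applies. The plan states no figure on this point, and no sample size or confidence bound depends on it. The check sets the rules side by side.

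**Step 1: does a laboratory value reach the SAE test at all?** Section 12.1 counts a laboratory value as an adverse event when the Investigator considers it clinically significant and it led to a medical intervention, a dose hold, a dose reduction or a schedule change. A Grade 4 value that leads to treatment in hospital would ordinarily qualify. It is then an adverse event to which the Section 12.3 criteria apply.

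**Step 2: apply both rules case by case.**

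| Grade 4 laboratory adverse event | Outcome criteria with 12.4.1 | Last sentence of 12.3 | Conflict? |
|---|---|---|---|
| (a) Meets no seriousness criterion | Not an SAE | Not reported as an SAE | No |
| (b) Accompanied by a clinical diagnosis recorded as an SAE | Reportable | Exception applies, reportable | No |
| (c) Itself requires admission or is an immediate risk of death; no associated diagnosis recorded as an SAE | SAE, due within 24 hours | Not reported as an SAE | Yes |

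Only case (c) conflicts. Case (a) is probably the commonest: grade measures severity, whereas the life-threatening criterion requires an immediate risk of death, so Grade 4 does not by itself meet it.

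**Step 3: does the exception rescue case (c)?** Clinical diagnosis is not defined. If a term such as thrombocytopenia does not count as one, the event is excluded. If it does count, the exception still requires that diagnosis to be a recorded SAE, so the event may be reported as an SAE provided it has already been recorded as one. That is circular. Neither reading refers back to the outcome criteria.

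**Step 4: compare adjacent grades.** The sentence names Grade 4 only. Table 2 describes Grade 3 hyperglycemia as above 250 and up to 500 mg/dL, and Grade 4 as above 500 mg/dL. A subject admitted for the Grade 3 event is an SAE under the hospitalization criterion, and nothing removes it. A subject admitted for the Grade 4 event, with no associated recorded SAE, falls under the exclusion. Read literally, the more severe event is the one not reported.

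**Step 5: trace what uses SAE status.**

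- Dependent on it: the 24-hour report (12.4.1), the IRB report (12.4.2), the SAE objective (7.2) and the serious TEAE table (14.4.4).
- Not dependent on it: objective response rate; TEAE tables by severity and by treatment modification; laboratory shift tables of worst grade; the listing of on-study deaths (14.4.4).
- Not dependent on it: Safety Review Committee input, which covers toxicity of Grade 3 or higher whatever its cause, discontinuations, dose reductions and deaths. The stopping guidelines in 9.3.2 do not use SAE status either.

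**The case against.** The best defence is that the closing sentence governs reporting, not definition, and is a specific exception to a general rule. On that view nothing is contradictory, and its likely purpose, to keep bare Grade 4 values from flooding the SAE system, is sensible. The text also asks only for an associated diagnosis, not a separate one. Section 12.2 encourages recording a diagnosis where possible, so a site could enter the admission as the SAE of thrombocytopenia or hyperglycemia and arguably satisfy the exception. The Sponsor may also judge an event serious under Section 12.3.

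Part of this stands. The wording does not force a separate diagnosis, the purpose is legitimate, and the Sponsor's own judgement is a partial safeguard. But reading the sentence as a deliberate exception means that hospitalized Grade 4 laboratory events are intentionally left out of SAE reports, which Section 12.4.1 does not allow. The associated-diagnosis reading is the circular one. If the intent was to exclude events on grade alone, the sentence does not say so.

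Three stronger readings are tempting, and the documents do not support them:

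- A reader might infer that Grade 4 laboratory events in general are both SAEs and not SAEs. Cases (a) and (b) show otherwise.
- A reader might infer that SAE incidence will be biased downward and will differ by site. Nothing in the documents shows how sites will read the sentence; the risk is possible, not established.
- A reader might want a number of affected subjects. The documents give no Grade 4 rate for this regimen. Section 6.3.1 pools Grades 3 and 4 across the Phase 1 study, its dose-limiting events arose on other schedules, and Section 6.1.3 reports none on the 60 mg 5/2 schedule. Any count would rest entirely on assumed rates.

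**Conclusion.** Wrong as written, and minor: a safety-reporting rule that can override the protocol's own seriousness criteria. It does so only for a Grade 4 laboratory adverse event that itself meets a criterion and has no associated clinical diagnosis recorded as an SAE. The conclusion rests on reading the sentence literally and on the event qualifying as an adverse event under Section 12.1.

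The consequence is possible omission of such events from expedited reports and from the serious TEAE table. They are not lost to the safety analysis, because they remain visible as graded TEAEs and in the shift tables. No numerical size can be given, and the finding does not need one.

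**What to change.** Reconcile the last sentence of Section 12.3 with the criteria above it and with Section 12.4.1. Suitable wording: *A Grade 4 laboratory abnormality is not an SAE on grade alone; it is reported as an SAE when it meets any of the seriousness criteria above.* This keeps the purpose of the exclusion, removes the undefined reference to a clinical diagnosis, and treats Grade 3 and Grade 4 events by the same test. Build the serious TEAE table in Section 14.4.4 on that definition.

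The cost is one sentence in an amendment and a note to sites. The downside is a few more SAE reports and a slightly less favourable SAE rate. No treatment rule and no efficacy analysis changes.

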## **12.4. Reporting of Adverse Experiences, Serious Adverse Experiences, Serious and Unexpected Adverse Experiences**

### **12.4.1. Reporting Adverse Events and Serious Adverse Events to the Sponsor**

All SAEs, regardless of relationship to the study treatment, must be reported to the Sponsor within 24 hours of the Investigator becoming aware of the event. Written SAE notification must follow within the 24-hour reporting timeframe, via an SAE Report submitted to Novella Clinical Safety Management via email at [[contact]](mailto:[contact]) or by fax at [name]. Where appropriate, follow-up SAE reports must be submitted by the Investigator as new information becomes available. All treatment-emergent SAEs should be followed until resolution, return to baseline or stabilization.

If the Investigator becomes aware of safety information involving a subject who participated in the study that appears to be drug related, even after an individual subject has completed the study, this should also be reported to the Sponsor.

### **12.4.2. Reporting to the Institutional Review Board (IRB)**

SAEs will be reported to the IRB by the Investigator according to local or national requirements and the IRB's policy and procedures.

### **12.4.3. Reporting to the Regulatory Authorities**

The Sponsor will be responsible for reporting all AEs and SAEs to the appropriate regulatory authority (e.g., U.S. FDA), Investigators, and central IRB in accordance with all applicable regulations and guidances.

#### **12.4.4. Pregnancy Reporting**

Pregnancy testing must be performed in all female subjects of childbearing potential at Screening, at least once per cycle prior to dosing, at the EOT visit, and as clinically indicated. In the event of a positive test result, subjects will be discontinued from study drug and will be followed for the outcome of their pregnancy.

If a female subject suspects she might be pregnant (e.g., missed or late menstrual period) or a male subject suspects he may have fathered a child at any time during the study through the final Follow-up visit, they must notify the Investigator immediately. The Investigator will follow the subject or subject's partner to determine the outcome of the pregnancy.

Information regarding pregnancy must be reported immediately to the Sponsor and the outcome information provided once the outcome is known.

The Investigator should complete the Initial Pregnancy Notification report form and forward it to the Sponsor (or designee) within 24 hours of knowledge of the pregnancy. If there is an associated serious outcome, then both the Initial Pregnancy Notification report form and SAE report form should be completed.

The Investigator should follow-up with the subject or subject's female partner until delivery or termination of pregnancy even if the subject was withdrawn from the clinical study or if the clinical study has finished. At that time, the Pregnancy Outcome report form should be completed and submitted to the Sponsor within 24 hours after the Investigator becomes aware of the pregnancy outcome.

In the event the pregnancy outcome occurs following the end of the study and database lock, the Investigator will report the pregnancy outcome to the Sponsor (or designee) within 24 hours after the outcome of the pregnancy is known to the Investigator in accordance with the procedure for reporting SAEs (see Section [12.3](#)).

### 13. STUDY ACTIVITIES

During the treatment period, all treatment assessments/procedures should occur within  $\pm 2$  days of the scheduled time points. If extenuating circumstances prevent a subject from starting or completing treatment, or a scheduled procedure or assessment within the protocol-specified time, the subject may continue to be treated on the study only with permission of the Curis Medical Monitor or designee clinician.

All times should be recorded using the 24-hour clock (e.g., 23:20, rather than 11:20 PM).

#### 13.1. Prescreening (Before Day -28) and Screening (Days -28 to -1)

The following procedures may be performed between Days -28 and -1:

- Informed consent
  - Based on local site requirements, the following ICF procedures are acceptable:
    - An ICF specific for MYC testing will be signed before the tumor sample is sent for central testing (Prescreening).
    - The main ICF will be signed to begin the Screening period (Day -28 to Day -1).
- Review inclusion/exclusion criteria
- Subject demographics, medical history, and medication history
- Obtain archival or fresh tumor sample (preferred) for central FISH and IHC testing and review
  - If archival, it must be the most recently available tumor sample
  - Fresh tumor tissue should be obtained from biopsy-accessible lesions with low estimated risk for serious complications (less than 2%)
  - Local MYC results performed previously should be entered into the eCRF at screening although central testing is required for all patients
- IPI score
- Radiologic assessment (CT/MRI and FDG-PET/CT, if applicable)
- Urinalysis
- Collect plasma for biomarker sampling
- Optional tissue collection for biomarker sampling (from subjects with accessible tumor lesion) (may be obtained anytime up to pre-dose Cycle 1, Day 1)
- Pharmacogenomic sampling
- Update concomitant medications

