## 5. SCHEDULE OF EVENTS

### 5.1. Schedule of Events

Assessments	Screening		Treatment Period (21-Day Cycles) 							Post-Treatment		
	Days -28 to -1	Days -7 to -1	Cycle 1					Cycle 2-6	Cycle 7+	EOT	F/U ≤ 6 months	F/U > 6 months
			Day 1 	Day 5	Day 8	Day 12	Day 15	Day 1 	Day 1 	D30 ± 7d post last dose	q12 weeks ± 1 week	q24 weeks ± 2 weeks
Informed consent	X											
Inclusion/exclusion	X											
Medical and medication history/demographics	X											
Archival/fresh tumor tissue 	X											
Physical examination 		X	X					X	X	X		
Symptom-directed physical examination				X		X					X 	X 
ECOG performance status		X	X					X	X	X		
IPI score	X										X	X
Height		X										
Vital signs 		X	X	X		X		X	X	X		
ECG		X								X		
Pregnancy test 		X	X					X	X	X		
Lymphoma assessment 			X					X	X	X 	X 	X 
Radiologic assessment  (CT/MRI)	X 							X 	X 	X 	X 	X 
Radiologic assessment  (FDG-PET/CT)	X 							X 	X 	X 	X 	X 
Survival status 											X	X
CBC w/diff		X	X	X		X		X	X	X		
Chemistries 		X	X	X		X		X	X	X		
Urinalysis	X											
Plasma for biomarker sampling	X							X	X			
Plasma for PK sampling 			X		X 		X 	X	X			

Tissue for biomarker sampling 	X						X						
Pharmacogenomic sampling	X												
Concomitant medications	X	X	X	X			X	X	X	X	X 	X 	
Adverse events			X	X			X	X	X	X	X 	X 	
CUDC-907 dosing			5 days on/2 days off 										

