### **7.3. Exploratory Objectives**

- To explore the effects of CUDC-907 on disease-associated biomarkers.
- To explore the relationship between disease-associated biomarkers in plasma and tumor tissue. Among biomarkers of interest, BCL2 and BCL6 protein expression and translocation status in particular will be tested in tumor tissue, where possible.
- To explore biomarkers of response for patient selection.
- To explore the relationship between additional biomarkers and biomarker profiles that may influence biologic and clinical responses to CUDC-907.
- To explore the ORR according to Lugano classification ([Cheson et al, 2014](#); [Barrington et al, 2014](#)).

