## 9.2. Patient Exclusion Criteria:

1. Known primary mediastinal, ocular, epidural, testicular or breast DLBCL.
2. Patients must not have active CNS involvement of their malignancy. Patients with prior brain metastases are permitted, but must have completed treatment and have no evidence of active CNS disease (clear cerebrospinal fluid [CSF]) for at least 4 weeks prior to the first dose of CUDC-907. Intrathecal chemoprophylaxis to prevent the emergence or recurrence of lymphoma in the CNS is permitted on study and may be administered per institutional guidelines.
3. Known allergy or hypersensitivity to PI3K inhibitors or any component of the formulations used in this study.
4. Cytotoxic anticancer therapy (e.g., alkylating agents, anti-metabolites, purine analogues) within 2 weeks of study entry.
5. Radiotherapy delivered to non-target lesions within one week prior to starting study treatment or delivered to target lesions that will be followed on the study (note: prior sites of radiation will be recorded).

6. Treatment with experimental therapy within 5 terminal half-lives ( $t_{1/2}$ ) or 4 weeks prior to enrollment, whichever is longer.
7. Current or planned glucocorticoid therapy, with the following exceptions:
  - Doses  $\leq 1$  mg/kg/day prednisolone or equivalent glucocorticoid and inhalational therapies for mild chronic obstructive pulmonary disease (COPD) or asthma are allowed.
  - Replacement dosing of steroids (defined as  $< 30$  mg/day hydrocortisone or the equivalent) is allowed, provided that the steroid dose has been stable or tapering for at least 14 days prior to the first dose of CUDC-907.
8. Graft versus host disease following transplant within 100 days prior to study treatment.
9. Major surgery, other than diagnostic surgery, occurring 4 weeks prior to study treatment.
10. Diabetes mellitus that is not controlled with medication.
11. Serious infection requiring intravenous antibiotic therapy within 14 days prior to study treatment.

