### **11.5.2. Plasma Biomarker Assessments**

Blood samples (20 mL) for plasma biomarker analysis will be drawn during the Screening period and on Day 1 of scheduled clinic visits per protocol (see Schedule of Events in Section 5.1). The plasma samples will be analyzed for cell-free DNA (cfDNA) and potential markers of CUDC-907 activity, such as changes in cytokine levels.

These time points may be administratively adjusted or discontinued at the discretion of the Sponsor; however, the total number of blood samples will not be increased.

Collection details and shipping address will be provided in the laboratory manual.

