#### **13.2.1. Cycle 1**

##### **13.2.1.1. Cycle 1, Day 1**

The following procedures will be performed on Cycle 1, Day 1:

- Physical examination
  - Note: The Cycle 1, Day 1 physical examination is not required if the Screening physical examination was conducted within 3 days prior to administration of the first dose of study drug (Cycle 1, Day 1).
- Update ECOG performance status
- Vital signs (blood pressure, heart rate, respiratory rate, temperature, and weight)
- Lymphoma assessment (includes physical examination, a review of the subject's current signs and symptoms, B symptoms, and concomitant medications)
- CBC with differentials

- Serum chemistries (sodium, potassium, magnesium, phosphate, total protein, chloride, bicarbonate, calcium, BUN, creatinine, uric acid, total bilirubin, alkaline phosphatase, AST, ALT, LDH, albumin, and glucose)
- Pregnancy test (women of childbearing potential)
- Collect plasma for PK sampling (2 hours post-dose)
  - CUDC-907 will be administered in the clinic on PK sampling days
- Update concomitant medications
- Collect AEs
- CUDC-907 dosing (CUDC-907 is taken PO for 5 days on/2 days off)

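### The only pre-treatment plasma biomarker sample may be up to 28 days old at first dose, so as much as 57% of the first change-from-baseline interval can be untreated

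*Combined protocol and SAP*

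**What the plan says.** Section 13.1 lists "Collect plasma for biomarker sampling" among procedures for which the only timing rule is "The following procedures may be performed between Days -28 and -1". The shorter block in Section 13.1.1, Days -7 to -1, does not repeat it.

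Section 13.2.1.1 opens with "The following procedures will be performed on Cycle 1, Day 1". The only plasma item there is pharmacokinetic: "Collect plasma for PK sampling (2 hours post-dose". No other Cycle 1 visit lists biomarker plasma. It next appears in Section 13.2.2.1, on Day 1 of Cycles 2 to 6.

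The Schedule of Events (Section 5.1) agrees. The row "Plasma for biomarker sampling" is marked under Screening Days -28 to -1, Cycles 2-6 Day 1 and Cycles 7+ Day 1, and is blank under Days -7 to -1 and every Cycle 1 column.

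Section 11.5.2 reads a little differently: samples "will be drawn during the Screening period and on Day 1 of scheduled clinic visits", with a reference back to the Schedule. It gives cell-free DNA and markers of drug activity, including cytokine changes, as the purpose. It also lets the sponsor adjust or drop these time points administratively, provided the total number of samples does not rise.

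The first exploratory objective in Section 7.3 is "To explore the effects of CUDC-907 on disease-associated biomarkers". No section says which sample is the plasma baseline or limits its age to less than the 28-day window.

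**The concern.** A change from baseline estimates what happened after dosing only if the baseline describes the subject at the time of dosing. Here the sample may describe the subject up to four weeks earlier. Section 6.1.1.1 describes untreated DLBCL as quickly fatal and cites median PFS in relapsed or refractory disease starting at 1 month, so four weeks is not obviously a negligible lag.

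Two things can happen between draw and dose. The disease can progress, which would partly hide a real fall in a tumour-related marker. The subject can also be recovering from, or still receiving, earlier treatment, which could move a marker in either direction. With a single pre-treatment sample, neither can be estimated afterwards or removed reliably. Since the draw day is left to scheduling, the amount of pre-dose time differs between subjects and adds variation unrelated to the drug.

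What is at stake is the interpretation of the exploratory plasma biomarker changes, and nothing beyond that.

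**Working it through.** The plan gives no figure to reproduce on this point. The check is a comparison of the sections, followed by day counts.

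**Inputs**
- Draw window: Day -28 to Day -1 (Sections 5.1 and 13.1).
- First on-treatment draw: Cycle 2 Day 1 (Sections 5.1 and 13.2.2.1).
- Cycle length: 21 days, so Cycle 2 Day 1 is nominally 21 days after first dose.
- Window for on-treatment procedures: ±2 days (Section 13), giving 19 to 23 days.
- Prior therapy (Section 9.2): radiotherapy to non-target lesions is barred in the week before study treatment starts; exclusion 4 bars "Cytotoxic anticancer therapy (e.g., alkylating agents, anti-metabolites, purine analogues) within 2 weeks of study entry".
- Convention assumed: no Day 0, so a draw on Day -d is d days before Day 1.

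**Untreated share of the first interval**

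Share = d / (d + t), where t is the number of days from first dose to Cycle 2 Day 1, including scheduled days off drug.

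| Draw day | Untreated days | Interval with t = 21 | Share | Share with t = 23 to 19 |
|---|---|---|---|---|
| -28 | 28 | 49 | 57.1% | 54.9% to 59.6% |
| -21 | 21 | 42 | 50.0% | 47.7% to 52.5% |
| -14 | 14 | 35 | 40.0% | 37.8% to 42.4% |
| -7 | 7 | 28 | 25.0% | 23.3% to 26.9% |
| -1 | 1 | 22 | 4.5% | 4.2% to 5.0% |

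At the nominal 21 days, the untreated part is the longer one only for draws before Day -21.

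**Overlap with prior therapy, for a Day -28 draw**
- Non-target radiotherapy: its limit counts from the start of study treatment, so it could be given up to 28 − 7 = 21 days after the draw.
- Cytotoxic therapy, if study entry means first dose: up to 28 − 14 = 14 days after the draw.
- Cytotoxic therapy, if study entry means consent or the start of screening: no overlap, although recovery from earlier treatment can still fall between draw and dose.

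**After the change**
- Pre-dose draw on Cycle 1 Day 1: about 0 of 21 days untreated.
- Draw up to 3 days earlier, as Section 13.2 allows for the Day 1 blood counts and chemistries: at most 3 / (3 + 21) = 3/24 = 12.5%.

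**The case against.** **No stated analysis uses this change.** Section 14 lists the biomarker items as exploratory and describes no biomarker analysis. The Synopsis speaks of baseline levels and/or changes, where feasible. Predictive uses need only a baseline level, and a full SAP is still to be finalised (Section 14.4). This stands as a limit on importance. It does not remove the point, because Section 11.5.2 gives changes in activity markers as a purpose, and a later analysis plan cannot repair the timing of samples already taken.

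**Section 11.5.2 may already cover Cycle 1 Day 1.** Read alone it could, since that is a scheduled clinic visit. But it defers to the Schedule, where the cell is blank. This shows a wording conflict that sites could resolve differently, and does not secure a Day 1 sample.

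**A Day -7 to -1 window would remove most of the gap.** It would cap the untreated share at 25%, using an existing screening block. That is a fair alternative, and it avoids the risk that a draw missed on Day 1 cannot be recovered.

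**Later samples help.** Plasma is drawn again at later Day 1 visits, so on-treatment trajectories do not rest on one pair. This is true, but every change from baseline still uses the same pre-treatment value.

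Four stronger readings are tempting and not supported:
- *That the changes are necessarily distorted.* The documents permit an early draw but do not require one.
- *That samples will be taken during chemotherapy.* This depends on what study entry means, which the protocol does not define.
- *That the bias can be given a size.* Assuming cell-free DNA doubling times of 14 to 42 days, growth over 28 days would be 2^(28/42) to 2^(28/14), or 1.6 to 4.0 fold. The documents give no doubling time or marker variability, so this is not an estimate for this trial.
- *That a Day 1 draw would isolate the drug effect.* Without a control arm, disease course during treatment remains mixed in.

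**Conclusion.** The point holds as an avoidable weakness in an exploratory component. The Schedule and Section 13 agree on a single pre-treatment plasma biomarker draw anywhere from Day -28 to Day -1, none on Cycle 1 Day 1, and the next on Cycle 2 Day 1. Followed as written, the untreated share of the first interval runs from about 5% to 57%, depending on when each subject happens to be sampled.

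Those shares rest on the protocol's own day counts, a nominal 21-day first cycle and no Day 0. The overlap with non-target radiotherapy follows directly from Section 9.2; the cytotoxic overlap is conditional on the meaning of study entry. Pre-dose change is possible rather than certain, and its effect on any marker cannot be computed from the documents. ORR, the secondary endpoints and the sample size do not use this sample. The change is worth making because it is cheap, not because the trial's main conclusions are at risk.

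**What to change.** In Sections 5.1, 11.5.2, 13.1 and 13.2.1.1:
- Move the pre-treatment plasma biomarker draw to Cycle 1 Day 1 and state that it is taken before the first dose. If some flexibility is needed, allow it no earlier than the 3-day window used for the Day 1 laboratory tests. Saying only that it is taken with those tests would not guarantee a same-day sample.
- Name this sample as the baseline for plasma biomarker changes.
- Reconcile Section 11.5.2 with the Schedule, so that both state whether Cycle 1 Day 1 is a biomarker draw.

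**Cost.** Protocol wording only. The draw moves to an existing visit and the number of samples is unchanged, which fits the adjustment Section 11.5.2 already allows. The downside is looser pairing with tissue or imaging obtained early in screening, which bears on the objective relating plasma to tumour markers. For tissue this is limited, because Section 13.1 allows the optional biomarker biopsy up to the time before dosing on Cycle 1 Day 1. A sample missed before the first dose cannot be replaced, so the visit instructions should make the order explicit.
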